## 4 STUDY OVERVIEW

### 4.1 Study Approach

[figure not shown]
**Treatment.** Preconditioning and cavity preparation are done using the Er:Cr:YSGG laser, Waterlase MD (mfg: Biolase Technology Inc, Irvine CA), and the gold hand piece with an MG6 fiber tip, trunk fiber, contra-angle hand piece. *Preconditioning.* Preconditioning is preformed using laser desensitization. One tooth will be randomly selected, and preconditioning will be performed using LLLT on the tooth with minimal tooth ablation. The LLLT settings that will be used for preconditioning are 0.25 Watts, 50 Hz, 0% water, 0% air, H mode. Following this a fiber-optic tip will be aimed perpendicular to the surface of the cervical portion of the tooth, ensuring that a 2mm distance will be maintained between the end of the fiber optic tip and the surface. The fiber-tip will be used to generate a 2mm line. The cavity on the second tooth will be prepared for without laser preconditioning. *Lesion Preparation – small preparations.* Small preparations are to be performed as follows. The Waterlase MD is set to 4.5W, 15 Hz, 65% air, and 60% water and the cavity is prepared according to the preferred technique. If patients indicate sensitivity, the procedure will be halted, patients fill out the VAS form and anesthetic will be offered. For patients who refuse anesthetic, the procedure will be continued at the same settings. *Lesion Preparation – small to medium preparations.* Small to medium preparations will be performed as follows. The Waterlase MD will be set to 2W, 15 Hz, 65% air, and 60% water and the cavity will be prepared according to the preferred technique. If patients indicate sensitivity, the procedure will be halted, patients fill out the VAS form and anesthetic will be offered. For patients who refuse anesthetic, the procedure will be continued at the same settings.

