**Restoration.** *Overall VAS Score.* Up to 3 intra-operative VAS measurements are recorded. If a patient feels even the slightest amount of pain during the procedure, they will be instructed to raise their hand and the treatment will be paused. The patient is then asked to fill in the VAS form before the procedure will be continued. After conclusion of the cavity preparation, patients will be asked to mark one last VAS rating indicating the overall pain of the procedure. Patients that do not raise their hand throughout the entirety of the procedure will be given an overall VAS rating of zero. Data for each patient will be recorded and analyzed in this way.

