### **Explanation of VAS analysis**

The VAS scale will be presented to the patients using a standard explanation (zero, indicating no pain at all, to 100, representing the ‘worst pain patient had ever felt’). Patients will be asked to place a vertical line on the VAS scale to indicate his/her discomfort status. They are encouraged to stop the treatment if they encounter any pain. The number of hand raises, as defined by the protocol, will be recorded and analyzed (small and medium/large preparations are analyzed separately), represent the number of times during the procedure the patient felt sufficient discomfort to stop the procedure.

VAS data will be assessed by the following assumptions: The 'lower' the average score, the 'better' the mode of treatment. Once the patient marks their vertical line on the scale, a precise measurement, in millimeters, was taken from the “zero” line of the VAS scale to where the patient marked their line.

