**Restoration:**

- Overall VAS Score: Up to 3 intra-operative VAS measurements are recorded. If a patient feels even the slightest amount of pain during the procedure, they are instructed to raise their hand and the treatment would be paused. The patient will then be asked to fill in the VAS form. The procedure could then be continued. After the conclusion of the cavity preparation, the patients are asked to mark one last VAS rating indicating the overall pain of the procedure.

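### Section 4.1 assigns an overall VAS of zero to patients who raise no hand, while 7.1 has them mark it; the rule can lower mean VAS or leave it unchanged, never raise it

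*Protocol*

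**What the plan says.** Three places in the protocol bear on the overall VAS of a patient who never raises a hand.

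- **Section 4.1, Restoration.** Patients mark a last VAS for overall pain once the preparation is finished. The next sentence reads: "Patients that do not raise their hand throughout the entirety of the procedure will be given an overall VAS rating of zero". The paragraph closes by saying that each patient's data are recorded and analysed on this basis.
- **Section 7.1, Restoration.** The workflow repeats the procedure: "After the conclusion of the cavity preparation, the patients are asked to mark one last VAS rating indicating the overall pain of the procedure". It contains no zero rule.
- **Section 4.1, Explanation of VAS analysis.** The score is a distance on the form: "a precise measurement, in millimeters, was taken from the" zero line to the patient's mark. The scale runs from 0 (no pain) to 100, and a lower average is read as the better treatment.

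The protocol also describes a hand raise in different ways. Section 4.1 sets a very low bar: "If a patient feels even the slightest amount of pain during the procedure, they will be instructed to raise their hand". The VAS explanation says "They are encouraged to stop the treatment if they encounter any pain", but then describes the count of raises as "the number of times during the procedure the patient felt sufficient discomfort to stop the procedure". Under Treatment in 4.1, a patient who indicates sensitivity sets off a sequence: "the procedure will be halted, patients fill out the VAS form and anesthetic will be offered".

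Sections 3 and 9.3 use the VAS forms to show that laser analgesia exists.

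**The concern.** A score that the patient is elsewhere asked to give is replaced by a fixed value, and only one of the two sections describing the procedure says so. Staff working from 7.1 and an analyst working from 4.1 could hold different values for the same tooth.

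The assigned value is also the most favourable one on the scale. It equals the true score only if every patient with any pain at all raised a hand. That is assumed, and the final mark, which is the one observation that could test it, is overridden. There are reasons to doubt full compliance: raising a hand interrupts treatment and brings an offer of anaesthetic, and the protocol itself describes raises as discomfort sufficient to stop. A patient with mild pain may prefer to carry on.

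At stake is the average overall VAS, which the study would cite as evidence of analgesia.

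**Working it through.** **1. The passages side by side.** Take a patient who raises no hand and would mark 8 mm at the end. Under 7.1 and the VAS explanation the score is 8. Under the rule in 4.1 it is 0. Nothing in the protocol says which prevails.

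**2. Direction.** The scale floor is 0, so replacing a mark x ≥ 0 by 0 changes it by −x ≤ 0. With q the share of teeth without a raise and m the mean that those patients would have marked:

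change in mean overall VAS = −q × m

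This is never positive, and it is zero only if q = 0 or m = 0. The protocol gives neither quantity. Over an assumed range, the fall in the mean is:

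| q | m = 0 | m = 2 mm | m = 5 mm | m = 10 mm |
|---|---|---|---|---|
| 0.25 | 0 | 0.5 | 1.25 | 2.5 |
| 0.50 | 0 | 1.0 | 2.5 | 5.0 |
| 0.75 | 0 | 1.5 | 3.75 | 7.5 |

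**3. An assumed model linking q and m.** All inputs here are assumptions: lognormal overall pain, patient median 12 mm (log SD 0.6), tooth-level log SD 0.53, capped at 100 mm, 2,000,000 simulated pairs. Patients raise a hand only if pain reaches a threshold, and values below it are set to 0. The mean without the rule is 16.39 mm.

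| Threshold (mm) | q | m (mm) | q × m (mm) | Mean with rule (mm) | Fall |
|---|---|---|---|---|---|
| 2 | 0.013 | 1.56 | 0.02 | 16.37 | 0.1% |
| 5 | 0.137 | 3.51 | 0.48 | 15.90 | 2.9% |
| 10 | 0.411 | 6.13 | 2.52 | 13.87 | 15% |
| 15 | 0.610 | 8.15 | 4.97 | 11.41 | 30% |
| 20 | 0.739 | 9.75 | 7.20 | 9.18 | 44% |

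For example, at 10 mm: 0.411 × 6.13 = 2.52, and 2.52 / 16.39 = 15%. If half the teeth are truly pain-free, the percentages are the same and the mean goes from 8.19 mm to 8.18, 7.95, 6.93, 5.70 and 4.59 mm.

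**4. The LLLT contrast.** The shift in the difference (LLLT minus no LLLT) is −(q_L × m_L − q_C × m_C), where L is the LLLT tooth and C the other. With m = 5 mm on both teeth:

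- non-raiser shares 0.6 and 0.4: −(3.0 − 2.0) = −1.0 mm, favouring LLLT;
- shares 0.4 and 0.6: +1.0 mm, against LLLT;
- equal shares: 0.

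In the model of step 3, with the LLLT tooth at an assumed 75% of control and the same threshold on both teeth, the reduction is 4.11 mm without the rule (SD 13.17, standardized 0.312). With the rule:

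| Threshold (mm) | Reduction (mm) | SD (mm) | Standardized |
|---|---|---|---|
| 2 | 4.13 | 13.19 | 0.313 |
| 5 | 4.40 | 13.57 | 0.324 |
| 10 | 4.71 | 15.13 | 0.312 |
| 15 | 4.53 | 16.42 | 0.276 |
| 20 | 4.08 | 17.04 | 0.239 |

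Intra-operative marks and hand-raise counts are not touched by the rule.

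**The case against.** The best defence is that 4.1 states a general instruction, then a specific exception, then says data are analysed that way. Section 7.1 omits the exception without denying it, and the VAS explanation only says how a mark is measured once made. Read so, there is one rule, and repeating it in 7.1 would cure the mismatch. Zero is also coherent in the protocol's own terms: patients are told, in 11.1 as well, to signal any pain, so no raise means no pain. The phrase about sufficient discomfort can be read to mean that any pain suffices.

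This stands as far as it goes: with full compliance there is no bias. But compliance is not verified, and repeating the rule in 7.1 would only extend an unchecked substitution.

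The sizes are also open to attack. They come from an assumed model that applies the threshold to the overall mark, whereas a raise responds to momentary pain. If peak pain is 1.5 or 2 times the overall mark (again an assumption), the fall at a 10 mm threshold is 6.3% or 2.9% rather than 15%, and at 20 mm it is 25% or 15% rather than 44%. Section 6.1.2 also leaves out of the study procedures finished under injection, so the modelled mean does not describe the analysed group. These points stand, and the figures are illustrations only.

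Finally, no VAS threshold defines analgesia and there is no non-laser comparator, so a lower mean triggers no stated decision. That limits the consequence. It also means that the absolute level of the VAS has to carry the claim of analgesia, and that level is what the rule can lower.

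**Conclusion.** The concern holds and should be fixed. Two things are certain from the text: the protocol yields two different overall scores for a patient who raises no hand, and the rule in 4.1 can only lower the mean overall VAS or leave it unchanged. Since a lower mean counts as better, any error supports the study's conclusion.

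The size is not known. It is q × m: nil if every patient with pain signals it, negligible if patients raise a hand at about 2 to 5 mm, and substantial (15% or more in the assumed model) if they tolerate 10 mm or more on the overall scale. The protocol gives no basis for choosing among these. For LLLT against no LLLT, the rule has no fixed direction.

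**What to change.** - Delete the zero-assignment sentence in 4.1.
- State in both 4.1 and 7.1 that every patient marks the end-of-procedure overall VAS for each tooth, whether or not a hand was raised; that this measured mark is what is analysed; and that a mark not made is recorded as missing.
- Analyse hand raises as a separate count, as the VAS explanation already foresees.
- Reconcile the wording in 4.1, the VAS explanation and 7.1 on what a hand raise represents.

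The cost is one sentence deleted and a few short statements added. The final mark is already part of the procedure, so patients who raise no hand make at most one extra mark per tooth. Patients without pain will mark zero, so true zeros are kept. The mean VAS may look less favourable.

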### **Explanation of VAS analysis**

The VAS scale will be presented to the patients using a standard explanation (zero, indicating no pain at all, to 100, representing the ‘worst pain patient had ever felt’). Patients will be asked to place a vertical line on the VAS scale to indicate his/her discomfort status. They are encouraged to stop the treatment if they encounter any pain. The number of hand raises, as defined by the protocol, will be recorded and analyzed (small and medium/large preparations are analyzed separately), represent the number of times during the procedure the patient felt sufficient discomfort to stop the procedure.

VAS data will be assessed by the following assumptions: The 'lower' the average score, the 'better' the mode of treatment. Once the patient marks their vertical line on the scale, a precise measurement, in millimeters, was taken from the “zero” line of the VAS scale to where the patient marked their line.

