## 3 STUDY OBJECTIVES

The principal objective of this study is to prove the phenomenon of laser analgesia. Traditionally before a cavity preparation is performed, the doctor will use local anesthetic (Needle Injection) before using rotary instrument to do a cavity preparation. The study involves using the Er,Cr=YSGG Laser to perform cavity preparation without giving any injection anesthesia. VAS (Visual Analog Scale) will be used to have patients rate the laser

cavity preparation procedure to show there is laser analgesia. On each patient subject that has two similar size cavities of the same classification, either Class I or Class V, on similar teeth. Two different laser protocols will be used. One includes Low Level Laser Therapy (LLLT) to condition the pulp producing analgesia before using higher power to perform the cavity prep. The other protocol will skip the LLLT setting and prepare the cavity with the higher power to perform the cavity prep. The design of the study is to find out if there is laser analgesia and if LLLT makes a difference in providing better analgesia. The VAS forms from each procedure will be used to show there is laser analgesia and potentially cavity preparations can be performed by using the laser without the need to give injection anesthesia first.

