## **9.3 Planned Analyses**

The clinical study report will contain only information necessary to prove this phenomenon.

Statistical analysis will include the VAS forms from each procedure which will be used to show there is laser analgesia and potentially cavity preparations can be performed by using the laser without the need to give injection anesthesia first. The VAS form is used to show how much pain they are in and if any. All patient data will remain anonymous during analyses to maintain patient confidentiality.

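### Section 9.3 limits the study report to results that support the claim, while VAS and hand raises are both to be analysed and no single VAS measure is designated for the LLLT comparison

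*Protocol*

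**What the plan says.** Section 3 poses two questions: "The design of the study is to find out if there is laser analgesia and if LLLT makes a difference in providing better analgesia". It ties the first to VAS: "The VAS forms from each procedure will be used to show there is laser analgesia".

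Section 4.1 describes how VAS is collected on each tooth. "Up to 3 intra-operative VAS measurements are recorded", one at each pause, and at the end "patients will be asked to mark one last VAS rating indicating the overall pain of the procedure". A further rule links VAS to the pauses: "Patients that do not raise their hand throughout the entirety of the procedure will be given an overall VAS rating of zero".

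The Explanation of VAS analysis in Section 4.1 gives a direction of benefit for VAS: "VAS data will be assessed by the following assumptions: The 'lower' the average score, the 'better' the mode of treatment". It also commits to a second outcome: "The number of hand raises, as defined by the protocol, will be recorded and analyzed (small and medium/large preparations are analyzed separately"). It gives no direction of benefit for that count.

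Section 9.3 opens with "The clinical study report will contain only information necessary to prove this phenomenon". It then says that the analysis will include the VAS forms. It mentions neither the hand raises nor the comparison of LLLT with no LLLT.

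**The concern.** The first sentence of 9.3 is a positive instruction about what goes into the report, and its criterion is support for the claim. A protocol should fix the reported results before the data are seen. Here the content depends on how the results turn out.

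The rule matters more because there is more than one result to choose from. VAS and hand raises measure related but different things. One severe pause gives a high rating and a single raise, while several mild pauses give low ratings and several raises. Within VAS, up to three ratings during the procedure and one overall rating are available, and the text does not say which of them the average score refers to. If the results differ, the rule allows the report to show the favourable one and omit the other. A reader could not then tell how many analyses lay behind the published result.

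**Working it through.** **The plan's own figure.** The only confidence level in the protocol is the 95% in Section 9.1, so I checked what it belongs to. The formula there is n = c²·N·p(1−p) / [A²·N + c²·p(1−p)], with c = 1.96, N = 50, p = 0.50 and A = 0.025.

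- Numerator: 3.8416 × 50 × 0.25 = 48.02
- Denominator: 0.000625 × 50 + 3.8416 × 0.25 = 0.03125 + 0.9604 = 0.99165
- n = 48.02 / 0.99165 = 48.42, as stated

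The worked line prints 1.69 in the numerator, which would give 36.00. The stated result needs 1.96 in both places. The formula is for estimating a proportion in a finite population. The 95% is therefore not attached to any test of VAS or hand raises, and the sample size does not show which outcome decides.

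**The passages side by side.**

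| Place | VAS | Hand raises |
|---|---|---|
| Section 3 | Named as the means of showing analgesia | Not named as an outcome |
| Section 4.1, Explanation of VAS analysis | Analysed; lower is better | Analysed by size group; no direction given |
| Section 9.3, analysis | Included | Not mentioned |
| Section 9.3, report | Only if it helps prove the phenomenon | Only if it helps prove the phenomenon |

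The last row holds whatever the ranking of the two outcomes.

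**What the freedom to choose could cost.** Assumptions: no LLLT effect; one VAS test and one hand-raise test, each two-sided at 5%; test statistics bivariate normal with correlation r; either result could be used.

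For independent outcomes:
- At least one false positive in either direction: 1 − 0.95² = 9.75%
- At least one false positive favouring LLLT: 1 − 0.975² = 4.94%

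For correlated outcomes the same probabilities come from the bivariate normal distribution:

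| r | Either direction | Favouring LLLT |
|---|---|---|
| 0 | 9.75% | 4.94% |
| 0.5 | 9.07% | 4.54% |
| 0.7 | 8.35% | 4.17% |
| 0.9 | 7.04% | 3.52% |
| One outcome only | 5.0% | 2.5% |

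The rule that assigns an overall rating of zero when no hand is raised makes the outcomes positively dependent, so the r = 0 row is an upper bound for two tests. The protocol's question is whether LLLT gives better analgesia, so the right-hand column is the relevant one. Testing hand raises separately by size group would add a test and raise the figures. I have not counted that, because the protocol gives no group sizes.

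**The case against.** The strongest objection is that the protocol does not treat the outcomes as equals. Sections 3 and 9.3 both name the VAS forms as what will show analgesia, and only VAS has a stated direction of benefit. Hand raises as an analysed outcome appear in one sentence, with no test and no link to an objective. A formal ranking or a split of the significance level is detail that a statistical analysis plan could supply. All of this stands. A reader might infer that VAS and hand raises are rival primary outcomes and that either alone can carry the claim. The documents do not support that, because nothing says hand raises alone can establish analgesia.

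It can also be said that the phenomenon in 9.3 is laser analgesia itself, with LLLT as a separate question. That is a fair reading of Section 3, but it does not rescue the sentence. The rule still filters the analgesia results by whether they support the claim, and it gives no assurance that the LLLT comparison will be reported.

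Nor can a statistical analysis plan cure the reporting rule. It could name a primary outcome, but the sentence would still stand in the protocol.

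**Conclusion.** The point holds as a fault in the reporting rule, made worse by an incomplete definition of the deciding VAS measure. As written, 9.3 permits an unfavourable VAS or hand-raise result to be left out. The protocol leans to VAS but does not designate one VAS measure for the LLLT comparison.

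The size is moderate: about 3.5% to 4.9% for a false result favouring LLLT, against 2.5% for a single outcome, or 7% to 9.8% against 5% in both directions. This rests on an assumed two-sided 5% level, on correlations from 0 to 0.9, and on the premise that either outcome could be used.

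Two stronger readings should not be drawn. One is that a 95% certainty promised for the LLLT claim is broken; the 95% in Section 9.1 belongs to the sample-size formula for a proportion. The other is that the protocol supports two opposite conclusions. With no effect, the two differences point in opposite directions in about a third of simulated trials at correlation 0.5, but these are mostly non-significant differences. Both outcomes being significant in opposite directions has probability of only about 0.001 at correlation 0 and 0.00001 at 0.5.

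**What to change.** Replace the first sentence of Section 9.3 with:

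*The report will give the VAS and hand-raise results for both the LLLT and the no-LLLT tooth, whatever their direction.*

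In the same section, state that the LLLT comparison is decided by the within-patient difference in the end-of-procedure overall VAS, and that hand raises are supportive. This also settles what the average score in the Explanation of VAS analysis means. The test and its level can be left to the statistical analysis plan.

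The cost is two or three sentences, with no new data, patients or procedures. The small downside is that a favourable hand-raise result alone can no longer support the claim.

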### **4.2 Study Duration**

The duration of this study will be conducted until all data is collected from the number of participants needed to complete this study.

## **5 STUDY POPULATION**

### **5.1 Sample Size and Target Study Population**

#### **5.1.1 Sample size**

The total number of individual subjects is expected to reach approximately forty-eight patients. This estimate is based on the number of teeth that possibly will need to have this surgery out of the people that come to the office.

### **5.1.2 Study population**

The study population will be representative patients that include adults 19-65 years old who had at least two cavity preparations of the same type, with the same approximate size lesion. Excluded patients include children, pregnant women, immune compromised patients, patients with heart disease, uncontrolled hypertension, cardiac arrhythmia, patients whose teeth amalgam restorations were in close proximity to the lesion, decay that has reached the pulp where potential for root canal therapy, patients of different language difficulty, and special/vulnerable patient populations will be excluded. Contradictions in device labeling is also include in the exclusion.

